7.1. Efficacy Hypotheses

Not applicable.

7.2. Analysis of the Primary Efficacy Parameters

7.2.1. Primary Efficacy Analysis

The primary endpoint of the study is ORR in Cohort A. Objective response rate is defined as the proportion of participants who achieve a BOR of CR or PR, based on RANO ([Wen et al 2010](#)), as assessed by an independent centralized radiological review committee. Confirmation of CR and PR is required and documented in the Independent Central Review Charter. This primary analysis of ORR will be based on the FAS. Participants who do not have sufficient baseline or on-study response assessment information to be adequately assessed for response status will be included in the denominators in the calculation of ORR. The 95% CI for the ORR will be estimated using the Clopper-Pearson method.

7.2.1.1. Response Criteria

Overall disease status will be categorized using RANO ([Wen et al 2010](#)). Participants will have their overall response evaluated as CR, PR, SD, PD, or NE at each postbaseline radiological assessment. Assessments using RANO are based on changes in enhancing measurable lesions, enhancing nonmeasurable/nontarget lesions, nonenhancing on T2-weighted or fluid-attenuated inversion recovery imaging (T2/FLAIR)/nontarget lesions, new lesions, steroid use, and clinical status.

7.2.1.2. Objective Response Rates and Best Overall Response

A participant is considered an objective responder if they have a BOR of CR or PR at any postbaseline visit before first PD.

In general, under RANO, BOR is the best response recorded postbaseline, before and including the first PD, in the order of CR, PR, SD, PD, and NE. The BOR will be determined from response assessments before or on the same day as new anticancer therapy. If any alternative cancer therapy, including palliative surgery and radiotherapy, is taken while on-study, then any subsequent assessments will be excluded from the BOR determination.

In the case of SD, measurements must meet the SD criteria at least once after the date of first dose at a minimum interval of 42 days. Participants who fail to meet this criterion will have either BOR of PD, if the next available assessment indicates PD or BOR of NE, if there is no additional assessment available.

7.2.2. Subgroup Analyses for Primary Endpoint

Subgroup analysis of the primary endpoint will be performed based on appropriate intrinsic and extrinsic factors if needed.

7.2.3. Sensitivity Analyses for Primary Endpoint

The primary endpoint will be analyzed using the PP population as a sensitivity analysis to the FAS.

7.3. Analysis of the Secondary Efficacy Parameters

7.3.1. Disease Control Rate

Disease control rate is defined as the proportion of participants who achieve a BOR of CR, PR, or SD, based on RANO ([Wen et al 2010](#)) and as assessed by an ICR. Confirmation of CR and PR is required and documented in the Independent Central Review Charter. This analysis will be based on FAS for participants in each cohort. Participants who do not have sufficient baseline or on-study response assessment information to be adequately assessed for response status will be included in the denominators in the calculation of DCR. The 95% CI for DCR will be calculated using exact method for binomial distribution in each cohort.

7.3.2. Progression-Free Survival

Progression-free survival is defined as the time from the date of first dose of pemigatinib to the date of the first documented progressive disease or death due to any cause, whichever is first. Progressive disease will be evaluated according to RANO ([Wen et al 2010](#)) and assessed by an ICR. Partial death dates will be handled using the rules described in Section [4.1.4](#). Participants who are alive without progression before the analysis cutoff date will be censored. Censoring for PFS will follow the algorithm outlined in [Table 2](#), which is based on the FDA guidance for industry ([FDA 2015](#), [FDA 2018](#)).

Table 2: Evaluation and Censoring of Progression-Free Survival

Situation	Outcome	Date of Progression or Censoring
No baseline tumor assessments	Censored	Day 1
No valid postbaseline response assessments	Censored	Day 1
Progression documented between scheduled response assessments	Progressed	Date of first overall response of PD
No progression	Censored	Date of last valid radiologic assessment (not NE and not missing)
Study discontinuation for undocumented progression	Censored	Date of last valid radiologic assessment (not NE and not missing)
Study discontinuation for toxicity or other reason	Censored	Date of last valid radiologic assessment (not NE and not missing)
New anticancer treatment including palliative surgery and radiotherapy started	Censored	Date of last valid radiologic assessment (not NE and not missing) on/before starting a new anticancer treatment
Death before first progressive response assessment	Progressed	Date of death
Death between adequate response assessments	Progressed	Date of death
Death or progression after 2 or more missed assessments	Censored	Date of last valid radiologic assessment (not NE and not missing)

This analysis will be based on FAS. Progression-free survival data will be analyzed by the Kaplan-Meier method in Cohorts A and B, respectively. The number of participants who progressed or died and the number of participants censored will be summarized. The Kaplan-Meier curves for PFS will be presented by cohort. The Kaplan-Meier estimate of median PFS will be presented with its 95% CI. The 95% CI will be calculated using the generalization of Brookmeyer and Crowley's method (1982) with log-log transformation (Klein and Moeschberger 1997).

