6.6.1. Restricted Medications and Procedures

Pemigatinib is predominantly metabolized by CYP3A4. There is an expected 50% increase in exposure in participants who concomitantly use CYP3A4 moderate inhibitors. However, as doses above the recommended Phase 2 dose of 13.5 mg QD have been tested (20 mg QD is tolerable), there is a sufficient safety margin. The use of moderate CYP3A4 inhibitors (see [Appendix D](#)) should be avoided; however, if unavoidable, the pemigatinib dose should be reduced from 13.5 mg to 9 mg or from 9 mg to 4.5 mg. If concomitant use of a moderate CYP3A inhibitor is discontinued, the pemigatinib dose can be increased (after 3 plasma half-lives of the CYP3A inhibitor) to the dose that was administered before starting the moderate inhibitor. The use of potent CYP3A4 inhibitors and inducers are prohibited (see Section [6.6.2](#)).

In certain instances, palliative surgery or radiotherapy to specific lesions is permitted if considered of benefit and medically necessary by the investigator. The sponsor must be notified if palliative surgery or radiotherapy is started; for any palliative radiotherapy or non-disease-related surgeries, the medical monitor should be consulted on when to restart pemigatinib. The lesions treated with palliative surgery or radiotherapy can no longer be assessed as target lesions.

In general, investigators should manage a participant's care with supportive therapies as clinically indicated, per local standard practice. However, care should be taken to assess any concomitant medication for the potential to have adverse drug-drug interactions with study treatment, including potentially impacting CYP3A4 metabolism.

Careful monitoring is required when pemigatinib is concomitantly administered with OCT2 substrates such as dofetilide and metformin, mild or moderate CYP3A4 inhibitors or inducers, and proton pump inhibitors.

Calcium-based phosphate-binding medications should not be used due to a concern for soft tissue mineralization. Refer to the [IB](#) for further details.

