7. DISCONTINUATION OF STUDY TREATMENT AND PARTICIPANT WITHDRAWAL

7.1. Discontinuation of Study Treatment

7.1.1. Reasons for Discontinuation

Participants **must** be discontinued from study treatment for the following reasons:

- The participant becomes pregnant.
- Consent is withdrawn.

Note: Consent withdrawn means that the participant has explicitly indicated that he/she does not want to be followed any longer; in this case no further data, except data in public domain, may be solicited from or collected on the participant.

Participants may choose to discontinue study treatment and remain in the study to be followed for progression and survival.

- Further participation would be injurious to the participant's health or well-being, in the investigator's medical judgment.
- Unacceptable toxicity as noted in Section [6.5](#).
- The study is terminated by the sponsor.
- The study is terminated by the local health authority, IRB, or IEC.
- Disease progression has been reported by an ICR.
- Other antineoplastic treatment is initiated, not including palliative radiation.

A participant **may** be discontinued from study treatment as follows:

- If, during the course of the study, a participant is found not to have met eligibility criteria, the medical monitor, in collaboration with the investigator, will determine whether the participant should be discontinued from study treatment.
- If a participant is noncompliant with study procedures or study drug administration in the investigator's opinion, the sponsor should be consulted for instruction on handling the participant.

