8.2. Efficacy Assessments

8.2.1. Tumor Imaging

Objective assessment of tumor status is required using appropriate disease-specific techniques, and a central radiologic facility will be used to determine responses, which will be logged into the eCRF. Response Assessment in Neuro-Oncology (RANO) criteria will be used to assess tumor response and progression. Tumor assessment will consist of a brain MRI (alternative modalities [eg, CT scan] should not be substituted for an MRI). Further details can be found in the imaging manual.

The schedule for MRI assessments will be during screening (this will be considered the baseline scan), every 9 weeks (every 3 cycles), and then at EOT (if applicable). Every effort should be undertaken to ensure the scan is done within 7 days of Cycle 1 Day 1, especially in cases of rapid progression, to ensure that a true baseline is captured ([Ellingson et al 2022](#)). Imaging should continue in 9-week intervals regardless of delays in cycle starts. For participants showing a response, a confirmatory scan may be performed a minimum of 4 weeks from the previous scan (per RANO; [Wen et al 2010](#)). For participants showing a progression based on local radiologic review, treatment should not be discontinued until progression of disease has been determined by the ICR unless the principal investigator believes it is in the best interest of the participant to discontinue treatment before receiving confirmation.

For participants who discontinue treatment for reasons other than disease progression, every effort should be made to continue monitoring their disease status by radiographic imaging until the start of new anticancer therapy, documented disease progression by ICR, death, or the end of study, whichever occurs first.

[figure not shown]

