8.8.2. Post-Treatment Disease Follow-Up

Participants who discontinue study drug for a reason other than disease progression will move into the disease status follow-up period and should be assessed every 9 weeks \pm 7 days by radiologic imaging to monitor disease status. Every effort should be made to collect imaging information regarding disease status until:

- The start of new anticancer therapy: the start of the new treatment should be captured, but the participant should continue to have disease assessments until progressive disease (see below)
- Disease progression (confirmed by an ICR)
- Death
- The end of study

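### SAP Table 2 censors PFS and DOR at palliative radiotherapy that the protocol allows during ongoing pemigatinib, and no sensitivity analysis shows the effect

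*SAP*

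**What the plan says.** **Protocol.** Section 6.6.1 states that "palliative surgery or radiotherapy to specific lesions is permitted if considered of benefit and medically necessary by the investigator". For palliative radiotherapy it adds that "the medical monitor should be consulted on when to restart pemigatinib", so study drug is expected to resume. On imaging it says "The lesions treated with palliative surgery or radiotherapy can no longer be assessed as target lesions"; other lesions are not mentioned as lost to assessment. Section 7.1.1 lists, among the mandatory reasons to stop study treatment, "Other antineoplastic treatment is initiated, not including palliative radiation". Section 8.2.1 adds "Imaging should continue in 9-week intervals regardless of delays in cycle starts". Section 10.4.2 defines PFS to the first centrally reviewed progression or death from any cause and says that censoring follows an algorithm based on FDA guidance. It does not mention palliative treatment.

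**SAP.** Table 2 in Section 7.3.2 has the row "New anticancer treatment including palliative surgery and radiotherapy started". Its outcome is Censored, dated to the last valid scan on or before the new treatment. Two other rows make a death an event on its date: one for a death before any progressive assessment, one for a death between adequate assessments. No order of precedence is given. Section 7.3.3 applies the same algorithm to DOR. For best overall response, Section 7.2.1.2 says: "If any alternative cancer therapy, including palliative surgery and radiotherapy, is taken while on-study, then any subsequent assessments will be excluded from the BOR determination". Section 7.2.3 plans a sensitivity analysis for the primary endpoint only. Appendix A lists one PFS table and one DOR table (2.2.4 and 2.2.5), both on the full analysis set.

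**The concern.** The protocol and the SAP classify the same procedure differently. For treatment, palliative radiotherapy is an allowed measure during the trial regimen. For analysis, it ends the participant's PFS and DOR follow-up, backdated to the preceding scan. A progression read centrally at a later scheduled scan, with the participant on pemigatinib, is collected but not counted.

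Kaplan-Meier estimation assumes that censored participants go on to have the same risk as those still followed. The protocol's condition for palliative treatment is that the investigator considers it beneficial and medically necessary, so recipients may well be at higher risk than the rest. If so, censoring them lengthens the curve. There is no control arm in which the same distortion could offset it. DOR deserves particular care because it is read alongside the response rate and rests on few participants.

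**Working it through.** **1. The plan's own figures.** The documents give no PFS or DOR assumption, event count or rate of palliative treatment, so there is no figure to correct. The one powered figure concerns ORR in Cohort A. With n = 82, the smallest count whose Clopper-Pearson lower limit exceeds 15% is 20 (lower limit 15.6%), and P(X ≥ 20 | n = 82, p = 0.28) = 80.1%. That reproduces the stated 80% or so and has no bearing on this point.

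**2. One participant traced through the rules.** No progression so far; palliative radiotherapy between two scans; pemigatinib restarted; the 9-weekly scans continue.

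- *Central review reads progression at a later scan.* The new-treatment row censors at the scan before radiotherapy. The progression is not an event.
- *The participant dies without documented progression.* The new-treatment row says Censored. The row for a death before any progressive assessment says Progressed. Two programmers could code this differently and both be following the SAP.
- *Best overall response.* Later scans are discarded. This can remove a response but cannot add one, so it does not favour the drug.
- *Overall survival.* Section 7.3.4 does not censor at new treatment, so OS is unaffected.

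**3. Illustrative size for PFS.** Every input here is an assumption. Time to event T is exponential, with median 9, 13 or 18 weeks; 15% of events are deaths, seen at T; progression is seen at the next multiple of 9 weeks. A share of 5%, 10% or 20% receives radiotherapy at R = uT, with u uniform on (0.6, 1) for late timing or on (0, 1) for random timing. Those participants are censored at the last multiple of 9 weeks not after R, or at Day 1 if there is none. There is no other censoring. Later deaths are taken as lost, that is, the new-treatment row is assumed to govern. With 400,000 simulated participants per scenario, Kaplan-Meier PFS at 26 weeks is:

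| True median | All events counted | Late timing: 5% / 10% / 20% | Random timing: 5% / 10% / 20% |
|---|---|---|---|
| 9 weeks | 23.2% | 24.2 / 25.2 / 27.7% | 23.8 / 24.3 / 25.6% |
| 13 weeks | 36.3% | 37.5 / 38.9 / 41.8% | 37.0 / 37.8 / 39.6% |
| 18 weeks | 47.9% | 49.3 / 50.7 / 53.7% | 48.8 / 49.6 / 51.7% |

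The smallest shift is 23.8 − 23.2 = 0.6 points and the largest 53.7 − 47.9 = 5.8 points; with random timing the largest is 51.7 − 47.9 = 3.8. All shifts are upward. Events lost among 82 are 82 × 0.05 = 4.1, 82 × 0.10 = 8.2 and 82 × 0.20 = 16.4. Of the last figure, 16.4 × 0.15 = 2.5 are deaths, which would return as events if a death row governs.

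The SAP reports the median, which 9-weekly scanning makes jumpy. In these scenarios it either stays put (18.0 weeks throughout when the true median is 13) or moves by up to one scan interval (9.0 to 18.0, or 18.0 to 27.0). Medians set exactly on a scan date exaggerate this, so the 26-week figure is the steadier guide.

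**4. Scale.** Around 36.3%, the sampling half-width with 82 participants is 1.96 × √(0.363 × 0.637 / 82) = 1.96 × 0.053 = 0.104, or about 10 points. The shift lies within sampling error, but it goes one way.

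**5. DOR.** At the planned rate there are 0.28 × 82 = 23 responders, so one lost event is 1/23, about 4% of that sample. DOR was not simulated.

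**The case against.** The case for leaving Table 2 alone has real strength.

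*No contradiction of the protocol.* A reader might infer that Table 2 breaks the protocol's PFS definition, or that SAP 10.1 should have declared a change. The documents do not support this. Protocol 10.4.2 leaves censoring to an FDA-based algorithm and is silent on palliative radiotherapy; Table 2 supplies that algorithm. Any censoring rule sets aside some observed events. Whether a participant stays on drug is also a separate question from what the analysis should estimate. Continued scanning settles nothing either: Protocol 8.8.2 continues imaging after any new anticancer therapy, where censoring is not disputed here. This objection stands.

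*Not censoring has its own problems.* Inclusion criterion 8 and exclusion criterion 9 ask for at least 12 weeks after radiotherapy unless there is histopathological confirmation or new enhancement outside the field. The next scheduled scan falls at most about 9 weeks after palliative radiotherapy, inside that window, so an early progression may be radiation effect. Conversely, radiotherapy may itself delay progression, and not censoring would credit that to pemigatinib. It would therefore be too strong to say that the row must be replaced. This also stands, and is why the remedy is a second analysis.

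*Informativeness is not proven.* The documents do not say that palliative radiotherapy is given for clinical worsening. RANO here includes steroid use and clinical status (SAP 7.2.1.1), so some worsening may already count as progression before radiotherapy starts. Plausibly informative is as far as one can go.

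*Limited stakes.* PFS and DOR are secondary, SAP 3.2 calls all analyses exploratory, and listings of current radiotherapy, procedures, deaths and response by visit make affected participants traceable. True, but a listing does not show a reader what the curve would be under the other rule. The per-protocol population changes who is analysed, not how they are censored.

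**Conclusion.** The concern holds as a gap in the PFS and DOR analyses. Progressions read by central review after permitted palliative radiotherapy, with pemigatinib continuing, are not counted; the status of later deaths is undefined; and no planned analysis shows the consequence. A reader might conclude that such deaths are certainly lost, but Table 2 supports either coding.

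The direction is plausibly upward for both endpoints. The size is unknown. The range of about 1 to 6 points on 26-week PFS rests on an assumed 5% to 20% receiving palliative treatment, exponential event times, radiotherapy always preceding the event, and deaths being censored.

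The conflict is clearest for radiotherapy. Protocol 7.1.1 does not exempt palliative surgery, although Table 2 treats both alike. It would be wrong to read the point as inflating the primary endpoint: the response rule can only lower ORR, and OS is untouched.

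**What to change.** Keep the Table 2 row as the primary rule if preferred, and amend the SAP in three places.

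1. In Sections 7.3.2 and 7.3.3, add one PFS and one DOR sensitivity analysis that does not censor at palliative radiotherapy while pemigatinib continues and counts a later centrally reviewed progression or death as an event. Other Table 2 rows stay as they are, including censoring at new systemic therapy. Say how palliative surgery is handled; it can remain censored here. Note in the text that early progression after radiotherapy may reflect radiation effect, and that radiotherapy may itself delay progression.
2. Report, by cohort, the number censored for palliative surgery and for palliative radiotherapy.
3. State the precedence between the new-treatment row and the death rows, so that a death after palliative treatment has one outcome.

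The cost is two extra Kaplan-Meier tables, a count and a sentence, using data the trial already plans to collect. PFS and DOR may look slightly shorter in the sensitivity analysis. No clinical rule changes.

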7.3.3. Duration of Response

For objective responders, the DOR is defined as the time from the date that a participant first achieves CR or PR, until the date of first documented progressive disease or death, whichever is first. Responses and progressive disease will be evaluated based on RANO (Wen et al 2010) and assessed by an ICR. Partial death dates will be handled using the rules described in Section 4.1.4. Participants who are alive without progression before the analysis cutoff date will be censored. Censoring of DOR will follow the same algorithm as the censoring of PFS (see Section 7.3.2).

This analysis will be based on FAS. The DOR data will be analyzed by the Kaplan-Meier method in Cohorts A and B, respectively. The total number of responders, the number of participants who progressed or died, and the number of participants censored will be summarized. The Kaplan-Meier curves for DOR will be presented by cohort. The Kaplan-Meier estimate of median DOR will be presented with its 95% CI. The 95% CI will be calculated using the generalization of Brookmeyer and Crowley's method (1982) with log-log transformation (Klein and Moeschberger 1997).

7.3.4. Overall Survival

Overall survival is defined as the interval between the date of first administration of pemigatinib to the date of death (due to any cause). Date of death will be determined using the Death Report, the Survival Follow-Up, and the Participant Status eCRFs. Participants who are lost-to-follow-up or still alive at the time of analysis will be right-censored at the earlier of the date the participant was last known alive and the clinical data cutoff date for the analysis. The last known alive date is defined as the later of the last study visit date and the date the participant was last known alive from the Survival Follow-Up and Participant Status eCRFs. Partial death dates will be handled using the rules described in Section 4.1.4.

This analysis will be based on FAS. Overall survival will be analyzed by the Kaplan-Meier method in Cohorts A and B, respectively. The number of participants who died and the number of participants censored will be summarized. The Kaplan-Meier curves for OS will be presented by cohorts. Median survival will be estimated using the Kaplan-Meier method. The 95% CIs for median survival time will be calculated using the generalization of Brookmeyer and Crowley's method (1982) with log-log transformation (Klein and Moeschberger 1997).

